## Scientific Background

Lung transplantation is one of the fastest growing solid organ transplant procedures in the United States.[1] Over the past four decades, notable progress has been made in the success of lung transplantation due to advances in organ preservation, surgical techniques, availability of bridge treatments (e.g., ventilator support, extracorporeal membrane oxygenation), and new immunosuppressive regimens.[2] According to the most recent report from the International Society for Heart and Lung Transplantation (ISHLT), the overall 5-year survival rate for LTR is 53%. [2] Lung transplantation leads to extended survival and quality of life in persons limited by advanced lung disease[3-5] and, therefore, has become an established treatment option.

After transplant, lung function typically returns to near normal levels. [6-8] However, reduced physical function and an inactive lifestyle compromise this benefit. Prior to transplant, end-stage lung disease reduces ventilatory capacity.[9] Disabling dyspnea limits physical activity and exercise, causing low muscle mass and qualitative changes in large exercising skeletal muscle groups.[10] Thus, LTR are severely deconditioned when they come to transplant surgery. After transplant, skeletal muscle changes persist.[11] Side effects of immunosuppressive agents further reduce lean muscle mass, increase fatigue, and decrease motivation to stay active.[12] A systematic review of 18 studies evaluating loss of skeletal muscle mass, strength and function in LTR reported that quadriceps strength was reduced in the pre-transplant period (range, 49%-86% predicted; n = 455 patients), further reduced immediately after transplant (51%-72% predicted, n = 126), with variable improvement at 3 months after transplant (58%-101% predicted, n = 164).[13]

While improved lung function after transplant has the potential to improve physical function, there is consistent evidence of limitations in reaching this goal.[6, 14-16] To promote rehabilitation goals, LTR are advised to attend a PR program.[17-19] Whereas post-transplant medical management requires following an established protocol, participation in PR is elective to LTR's individual decision. Studies documenting PR outcomes in other populations, [20, 21] consistent with our experience, report that PR is underused. It enrolls about a half of those referred [20] and loses > 25% of those who enroll to attrition.[21] Attrition of LTR in our PR clinic was greater than 50%. Barriers include scheduling and travel requirements,[18] perceptual disincentives and, of concern to LTR on immunosuppressive regimens, group participation which risks exposure to infection. Further, and of primary interest to this study, we pose that characteristics inherent to PR programs impact long-term adherence to exercise in LTR. During PR, exercise occurs under close clinician supervision but, afterward, LTR are expected to continue exercise unsupervised at home while not feeling confident. Consequently, LTR have little opportunity to establish behavior patterns that promote continued, independent self-management of exercise. Importantly, behavioral strategies, essential to achieve exercise goals and sustain self-management of exercise and active lifestyle, are not the main focus of traditional PR programs.

Telerehabilitation (TR) offers a flexible and sustainable alternative with the potential to promote and sustain self-management of exercise in LTR. Defined as an application of tele-health to rehabilitation,[22] TR uses telecommunication and computing technology to assess patients and deliver interventions in remote locations.[23-25] RCTs have evaluated TR-focused interventions in other populations, e.g., knee arthroplasty, stroke, and supported benefits of TR.[26-28] No

RCT has evaluated the use of the TR in LTR nor have exercise interventions for LTR incorporated behavioral strategies for self-management of exercise.

## Study Objectives

[figure not shown]
The study aims to evaluate efficacy of a behavioral exercise intervention, Lung Transplant Go (LTGO) compared to enhanced usual care (EUC) in improving physical function, physical activity and blood pressure (BP) control in lung transplant recipients.

Primary Aim: Evaluate efficacy of LTGO in improving physical function and physical activity from baseline to 3 and 6 months post-randomization.

Secondary Aim: Evaluate efficacy of LTGO on BP control from baseline to 3 and 6 months post-randomization.

## Study Design & Methods

After completing a baseline assessment, lung transplant recipients (LTRs) were randomized 1:1 to either the LTGO or Enhanced Usual Care group. To achieve balance between groups for known differences in exercise capacity, a blocked randomization scheme stratified by sex, and length of transplant-hospital stay ( $\leq 2$  weeks or  $> 2$  weeks) was used as an indicator of hospital-associated deconditioning. The statistician was responsible for randomization.

After the start of Covid, all study activities were performed remotely for both groups, including intervention delivery, recruitment, consenting, assessment, and data collection. Outcome assessors were blinded to group assignments. Data collectors were trained to perform study assessments until they demonstrated competency. Quality control checks of inter-rater reliability between assessors were repeated every quarter and remediation was instituted to remedy any drift from the assessment protocol less than ( $r = .97$ ). Assessors were trained to abstract data

from the electronic health record using established code books. Inter-rater reliability was determined between two raters for every 10 records. Data safety and intervention fidelity were monitored regularly. Surveys and semi-structured interviews were used to determine the usability and acceptability of the LTGO intervention. Performance of all assessments and delivery of intervention sessions and phone calls were audio or video-recorded. Intervention fidelity was monitored for 10% of phase 1 exercise sessions per subject and all phase 2 phone calls. Data safety monitoring (DSM) meetings were held monthly by the PI and PD, and annually by PI, PD and medical monitor.

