## Eligibility Criteria

### Inclusion Criteria:

- 18 years of age or older
  - >4 weeks after the participant had lung transplant surgery
- Discharged from the hospital after your lung transplant surgery
- MD report of difficulty walking ¼ mile or climbing 10 steps without resting
- Medical monitor approves patient eligibility for participation

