### Exclusion Criteria:

- concurrent participation in a formal exercise program, e.g., pulmonary rehabilitation, during the active eligible study period with no plans to stop formal exercise
- having other chronic conditions that may severely limit participation in exercise training, i.e., cardiac, musculoskeletal or cognitive impairments
- does not have home internet or smart device with Bluetooth capabilities
- medical issue precluding participation
- declining to be asked screening questions, or declining an introduction to the research team to hear about research
- greater than 18 months post-transplant hospital discharge (time/scheduling delays, transportation issues, etc.)

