## Statistical Considerations

An intent-to-treat (ITT) design was used wherein all participants were analyzed in the groups to which they were randomly assigned, regardless of treatment received or protocol deviations. The projected sample size was 112 participants a priori to reach a final sample of 80 randomized subjects (40 per group) to achieve 80% power to detect an effect size as small as 0.64,  $\alpha=0.05$ , two-tailed, for measures of the difference between LTGO and EUC groups in change in physical function, physical activity, and blood pressure control between baseline and 3 and 6 months.

Phases of data analysis involved an initial screening of data followed by the primary analysis to address each specific aim. All the analyses, including exploratory data analysis and linear mixed model, will be conducted by using SAS (v. 9.4, SAS Institute, Inc., Cary, NC).

Standard descriptive summaries (e.g., means, standard deviation, percentiles, range) and graphical techniques (e.g., histograms, scatter plots) were generated. The distribution of key variables was examined to ensure that the proposed modeling techniques were suitable. The assumptions underlying planned analysis methods were checked, and appropriate data transformation were performed, if necessary. The two groups were compared with respect to baseline variables using Student t-test or Mann-Whitney U test for continuous variables; categorical variables were compared between two groups by using Chi-square test or Fisher's exact test to ensure that randomization resulted in equal distribution of important variables.

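### Entry spans just over 4 weeks after surgery to 18 months after discharge, yet time since transplant is neither a stratum nor a specified covariate: a modest, cheaply recovered loss of precision

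*Combined protocol and SAP*

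**What the plan says.** **Entry window.** The Inclusion Criteria admit recipients ">4 weeks after the participant had lung transplant surgery". The Exclusion Criteria remove those "greater than 18 months post-transplant hospital discharge".

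**Randomization.** Study Design & Methods says that participants "were randomized 1:1 to either the LTGO or Enhanced Usual Care group", using "a blocked randomization scheme stratified by sex, and length of transplant-hospital stay". Hospital stay is split at 2 weeks and serves as an indicator of deconditioning.

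**Background.** Scientific Background says that quadriceps strength was "further reduced immediately after transplant (51%-72% predicted, n = 126), with variable improvement at 3 months after transplant (58%-101% predicted, n = 164").

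**Analysis and power.** Statistical Considerations names a linear mixed model in SAS but lists no fixed effects or covariates, not even the stratification factors. It plans baseline comparisons of the two groups on important variables, without naming the variables or saying what follows from an imbalance. On sample size it says: "The projected sample size was 112 participants a priori to reach a final sample of 80 randomized subjects (40 per group"). The purpose it gives for this number is "to achieve 80% power to detect an effect size as small as 0.64". The test is two-sided at 0.05 and concerns change between baseline and 3 and 6 months.

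**The concern.** Outcomes are changes over 3 and 6 months from a baseline that can fall anywhere in the entry window. Someone enrolled at 5 weeks passes through part of the first 3 post-transplant months during follow-up; someone enrolled at 15 months does not. If function improves in those early months, as the background reports for quadriceps strength, two participants with the same baseline score can have different expected changes without any intervention effect.

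Neither stratum captures this. Length of stay is fixed at discharge and does not show how far recovery has gone when a patient enrols months later. The outcome's baseline value does not show it either. The plan's own reason for stratifying, known differences in exercise capacity, would extend naturally to time since transplant.

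Precision is at stake. Variation in change that comes from enrolment timing stays in the residual, and in a trial of 80 a chance excess of early enrollees in one arm can enlarge or mask the LTGO contrast. With no covariate named in advance, a later adjustment would be open to the charge of having been chosen after seeing the data.

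**Working it through.** **Inputs from the documents:** 40 per arm, standardized effect 0.64, two-sided alpha 0.05, 80% power, 1:1 allocation (Statistical Considerations; Study Design & Methods).

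**Inputs not in the documents, so assumed:** R², the share of variance of change explained by time since transplant (1% to 20%); p, the share enrolled early, meaning before about 3 months (12% to 50%); g, the extra natural gain of early enrollees (0.25 to 1.0 within-group SD).

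**Step 1. Reproduce the stated power.** Two-sample t-test: noncentrality = 0.64 × √(40/2) = 2.862, 78 degrees of freedom, critical value 1.991. Power is 80.7% (81.7% by the normal approximation). The plan's 80% reproduces.

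**Step 2. Power after adjustment.** If 0.64 is on the total SD of change, the adjusted effect is 0.64/√(1 − R²).

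| R² (assumed) | Adjusted effect | Power |
|---|---|---|
| 0 | 0.640 | 80.7% |
| 1% | 0.643 | 81.1% |
| 5% | 0.657 | 82.6% |
| 10% | 0.675 | 84.6% |
| 20% | 0.716 | 88.5% |

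Giving up two degrees of freedom (76 instead of 78) costs less than 0.1 percentage point.

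The plan does not say which SD underlies 0.64. If it already excludes variability due to enrolment timing, the unadjusted effect is 0.64 × √(1 − R²), and unadjusted power is 80.3%, 78.7%, 76.5% and 71.5% at R² of 1%, 5%, 10% and 20%. Adjustment then restores about 80.7%.

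**Step 3. What the R² range corresponds to.** With an early group of share p and extra gain g, R² = p(1 − p)g² / [1 + p(1 − p)g²].

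- p = 0.20, g = 0.25: 0.010/1.010 = 1.0%
- p = 0.20, g = 0.5: 0.040/1.040 = 3.8%
- p = 0.30, g = 1.0: 0.210/1.210 = 17.4%
- p = 0.50, g = 1.0: 0.250/1.250 = 20%

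If entry were uniform over roughly 76 weeks (78 weeks after discharge, plus about 2 in hospital, less the first 4), about 9/76 = 12% would enrol before week 13. With g = 0.5, R² is then 2.6% and power is 81.7%.

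**Step 4. Chance imbalance.** Splitting the early enrollees among 80 at random into two arms of 40 (hypergeometric):

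| Early share (assumed) | Arms differ by ≥15 points | Arms differ by ≥20 points |
|---|---|---|
| 20% | 16% | 5% |
| 30% | 22% | 9% |
| 50% | 26% | 12% |

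A 15-point imbalance shifts the contrast by 0.15 × g. For g of 0.5 to 1.0 this is 0.075 to 0.15 SD, or 12% to 23% of 0.64; for g of 0.25 it is 0.0375 SD, or 6%. This is the same noise as in step 2 seen in a single realized trial, so the two must not be added together.

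**The case against.** **Validity.** Randomization makes any imbalance in enrolment time random, and the standard error of the unadjusted test already includes it, so the type I error rate stays near 5%. This stands. A reader might infer bias or an inadequate sample size, but the documents support neither. The 0.64 has no stated SD source and may already allow for recovery variability.

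**Evidence.** A reader might also take the background to show large spontaneous recovery, and subtract the midpoints of the two ranges to size it. It does not support that. The improvement is described as variable, the ranges overlap between 58% and 72%, they come from different patient numbers (126 and 164), and rehabilitation is not separated from natural recovery. The same section says that skeletal muscle changes persist after transplant.

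**Scope.** It is tempting to say that every outcome is affected. The only evidence is for quadriceps strength, which the list of protocol changes says was not assessed. Carrying it over to chair stands and steps is reasonable; for balance, respiratory quality of life, moderate-to-vigorous activity and hypertension stage it is only plausible.

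**Timing.** Part of the early change precedes any possible baseline, because entry requires more than 4 weeks. Someone enrolled at week 5 reaches week 13 after 8 of 13 follow-up weeks, so not all of the 3-month window lies in the period described. No passage says that later enrollees are on a plateau or declining. The requirement for reported difficulty walking or climbing may also narrow the early-late contrast.

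**Preference.** The mixed model is unspecified altogether, and other covariates could be argued for. That is fair. The unnamed baseline comparisons might include time since transplant, so the accurate statement is that no adjustment is specified, not that adjustment is ruled out. What remains is that the entry criteria create a wide spread in this variable, the background gives a reason to expect it to matter, and it can be used at almost no cost.

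**Conclusion.** The point holds as a modest matter of precision and chance imbalance. The documents establish the wide entry window, strata limited to sex and hospital stay, and a mixed model without stated covariates. That time since transplant predicts change is a plausible inference from the background, strongest for chair stands and steps.

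The benefit rests on an assumed R². At 1% to 3% adjustment adds about one percentage point of power or less over 80.7%; at 5% to 10% it adds about 2 to 4 points; at 20% it adds about 8. The gain is material only towards the upper end. The change is still worth making because its cost is negligible across the whole range.

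**What to change.** In the linear mixed model for each primary outcome, add log(time from transplant surgery to baseline) as a single continuous covariate, together with its interaction with visit. State this functional form in the analysis plan before unblinded analysis, so that no choice of form is left open. If the analysis has already been done, report the adjusted model as a sensitivity analysis, labelled as added afterwards.

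The cost is one sentence in the plan and one degree of freedom per visit. It needs no new patients and no new data, since the surgery date is needed to apply the entry criterion. If the covariate proves weakly prognostic, there is little or no gain.

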## Eligibility Criteria

### Inclusion Criteria:

- 18 years of age or older
  - >4 weeks after the participant had lung transplant surgery
- Discharged from the hospital after your lung transplant surgery
- MD report of difficulty walking ¼ mile or climbing 10 steps without resting
- Medical monitor approves patient eligibility for participation

### Exclusion Criteria:

- concurrent participation in a formal exercise program, e.g., pulmonary rehabilitation, during the active eligible study period with no plans to stop formal exercise
- having other chronic conditions that may severely limit participation in exercise training, i.e., cardiac, musculoskeletal or cognitive impairments
- does not have home internet or smart device with Bluetooth capabilities
- medical issue precluding participation
- declining to be asked screening questions, or declining an introduction to the research team to hear about research
- greater than 18 months post-transplant hospital discharge (time/scheduling delays, transportation issues, etc.)

## Protocol changes to primary outcomes due to COVID

1. Primary Outcome: Physical function-Walking, Change is being assessed from baseline to 3 months

\* Protocol modification 06-24-2020: since COVID, alternate measures for 6MWT due to inability to conduct in-person outcome assessments were the 30 Second Chair Stand Test (see primary outcome 5 and 6) and Average Steps per Day

2. Primary Outcome: Physical function- Walking, Change is being assessed from baseline to 6 months using Avg Steps per Day

\*Protocol modification 06-24-2020: since COVID, alternate measures for 6MWT due to inability to conduct in-person outcome assessments were the 30 Second Chair Stand Test (see primary outcome 5 and 6) and Average Steps per Day

3. Primary Outcome: Physical function- Balance-Change is being assessed from baseline to 3 months using the Berg Balance Scale

4. Primary Outcome: Physical function- Balance-Change is being assessed from baseline to 6 months using the Berg Balance Scale

5. Primary Outcome: Physical function- Lower Body Strength-Change is being assessed from baseline to 3 months using the 30 Second Chair Stand Test

6. Primary Outcome: Physical function- Lower Body Strength-Change is being assessed from baseline to 6 months using the 30 Second Chair Stand Test

Primary outcome: Physical function- maximal exercise watts per Kg, Change is being assessed from baseline to 3 months during the Cardio Pulmonary Exercise Test (CPET)

\*Protocol modification- since COVID, the max ex watts per KG test was excluded from outcomes due to inability to conduct in-person outcome assessments and no alternative measure was available for the CPET. This modification does not appear in the primary outcomes change history.

\* Protocol modification-Physical function- Quadriceps Muscle Strength-outcome was never assessed as it was deemed redundant with the 30 Second Chair Stand Test. This modification does not appear in the primary outcomes change history.

7. Primary Outcome: Physical function- Respiratory-related quality of life, Change is being assessed from baseline to 3 Months using the St. George Respiratory Questionnaire (SGRQ)

8. Primary Outcome: Physical function- Respiratory-related quality of life, Change is being assessed from baseline to 6 Months using the St. George Respiratory Questionnaire (SGRQ)

9. Primary Outcome: Physical Activity-Minutes of Moderate to Vigorous Physical Activity Per Day, Change from Baseline to 3 Months using Actigraph

\*Protocol modification 06-24-2020: since COVID, due to inability to conduct in-person outcome assessments, the Actigraph or the International Physical Activity Questionnaire-S (IPAQ-S) were approved measures of physical activity. The actigraph devices were mailed to participants thus precluding the need to administer the IPAQ.

10. Primary Outcome: Physical Activity-Minutes of Moderate to Vigorous Physical Activity Per Day, Change from Baseline to 6 Months using Actigraph

\*Protocol modification 06-24-2020: since COVID, due to inability to conduct in-person outcome assessments, the Actigraph or the International Physical Activity Questionnaire-S (IPAQ-S) were approved measures of physical activity. The actigraphs were mailed to participants thus precluding the need to administer the IPAQ.

11. Secondary outcome: Blood Pressure Control, Change in stage of hypertension from baseline to 3 months
12. Secondary outcome: Blood Pressure Control, Change in stage of hypertension from baseline to 6 months

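### Should average steps per day, which replaced the six-minute walk test, be moved from physical function to physical activity?

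*Combined protocol and SAP*

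**What the plan says.** The Study Objectives section puts two domains into one aim: "Primary Aim: Evaluate efficacy of LTGO in improving physical function and physical activity from baseline to 3 and 6 months post-randomization".

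The section on protocol changes due to COVID then lists ten numbered primary rows, each measure appearing at 3 and at 6 months. The two walking rows are worded differently. The 3-month row reads "1. Primary Outcome: Physical function-Walking, Change is being assessed from baseline to 3 months" and names no measure. The 6-month row reads "2. Primary Outcome: Physical function- Walking, Change is being assessed from baseline to 6 months using Avg Steps per Day". Under each is the same note, dated 06-24-2020, saying that in-person assessment had become impossible and that the alternates to the six-minute walk test were "the 30 Second Chair Stand Test (see primary outcome 5 and 6) and Average Steps per Day".

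The chair stand has rows of its own, for example "Physical function- Lower Body Strength-Change is being assessed from baseline to 3 months using the 30 Second Chair Stand Test". The physical activity rows are "9. Primary Outcome: Physical Activity-Minutes of Moderate to Vigorous Physical Activity Per Day, Change from Baseline to 3 Months using Actigraph" and "10. Primary Outcome: Physical Activity-Minutes of Moderate to Vigorous Physical Activity Per Day, Change from Baseline to 6 Months using Actigraph". The note under those rows says that "the Actigraph or the International Physical Activity Questionnaire-S (IPAQ-S) were approved measures of physical activity", and adds that the devices were posted to participants.

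**The concern.** A six-minute walk test measures what a patient can do under test conditions. A daily step count measures how much the patient walks in ordinary life. The second can rise because behaviour changes while capacity stays the same, and that distinction matters for an intervention built on behavioural strategies. The plan puts its other daily amount, minutes of moderate-to-vigorous activity, under physical activity, and gives no reason for treating steps differently.

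Two things seem to be at stake. First, a favourable step result could be presented as improved physical function although no numbered row now names a walking test; the cardiopulmonary exercise test was dropped as well. Second, if the steps and the activity minutes come from the same posted device, one change in daily activity could appear as a finding in both primary domains. The plan does not name the step device, so this second point is an assumption.

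**Working it through.** **1. Which measure do outcomes 1 and 2 use?** Outcome 2 states steps per day. Outcome 1 is silent, but its note lists only two alternates and sends the chair stand to outcomes 5 and 6, where it is called lower body strength. If outcome 1 also used the chair stand, it would duplicate outcome 5 and would not match its own 6-month counterpart. Steps per day is the only sensible reading of both rows.

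**2. Count of rows by heading.**

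| Measure | Rows | Heading in the plan | If steps are moved |
|---|---|---|---|
| Steps per day | 1, 2 | Function | Activity |
| Berg Balance Scale | 3, 4 | Function | Function |
| Chair stand | 5, 6 | Function | Function |
| St. George questionnaire | 7, 8 | Function | Function |
| Moderate-to-vigorous minutes | 9, 10 | Activity | Activity |

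- As written: 2 + 2 + 2 + 2 = 8 function rows and 2 activity rows.
- Steps as a share of the function rows: 2/8 = 25%.
- Daily amounts as a share of all primary rows: (2 + 2)/10 = 40%.
- After a move: 6 function and 4 activity. At each time point the split goes from 4 + 1 to 3 + 2.
- Total primary rows: 10 before and 10 after.

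**3. Does the heading enter the design calculation?** The inputs, from Statistical Considerations, are 40 per group, effect size 0.64 (taken as standardised, since no standard deviation is given), two-sided alpha 0.05 and power 80%.

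- Normal approximation: n per group = 2 × (1.96 + 0.8416)² / 0.64² = 15.70 / 0.4096 = 38.3, rounded up to 39.
- Two-sample t-test: n = 39.3, rounded up to 40, which reproduces the plan. Power at 40 per group is 0.807.

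The same effect size and alpha are stated for function, activity and blood pressure alike. No term in the calculation refers to a domain, so the result is the same under either heading.

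**4. Does the heading enter a decision?** The documents give no domain score, no alpha allocated by domain and no rule that a domain succeeds when some of its rows do. Each row is a separate comparison of change between groups. Moving a row alters no estimate, test or confidence interval.

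**5. Is the boundary one the plan has drawn?** Neither term is defined. The physical function heading already includes respiratory-related quality of life from a questionnaire, which is not a performance test either. The heading is a broad one, and a sub-label of walking is a fair description of a step count. Steps at any intensity and minutes above an intensity threshold are also different quantities, even if one device records both.

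**6. If the device is shared.** Granting that assumption, the two measures would be correlated and their results should be read together. They would be equally correlated under one heading or two, so relabelling would not remove the overlap.

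**The case for a change.** The strongest argument for acting is that the plan itself separates ability from behaviour. The Scientific Background treats reduced physical function and inactivity as distinct problems, and the primary aim names function and activity separately. Against that background, an unexplained split between two daily amounts invites over-reading. Relabelling would cost only a few words, would add and drop no data, and would restrict claims rather than create them.

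Part of this stands. A step result should be interpreted as the amount of daily walking and read beside the activity minutes. It is not performance on a test. Outcome 1 and the step device should also be named when the results are reported.

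The rest does not carry the argument. The documents make no walking-capacity claim from steps, so barring one would bar something that is not planned. Moving steps while leaving the quality-of-life questionnaire under function would not make the domains coherent. Much of the text is in the past tense and refers to an outcome change history. A late regrouping of primary outcomes could put the report out of line with that record, and would itself need explaining. The forced substitution is already open to view, with its date, its reason and both alternates given under each row.

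**Conclusion.** No change to the plan is needed. The facts behind the concern are right: 2 of the 8 rows headed physical function rest on a daily step count, outcome 1 names no measure, and no step device is stated. The choice of heading, however, affects no estimate, test, sample size, power or success rule. At most it affects the tone of one paragraph in the report.

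The gaps are of the kind that an analyst fills without difficulty. Outcome 1 is change in average steps per day, by its note and by its match with outcome 2. The chair stand counts in outcomes 5 and 6. The device is a detail for the methods section. Whether steps sit under function or activity is an interpretive choice with reasonable arguments on each side, and changing it late has a cost.

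This conclusion rests on two readings: that outcome 1 uses the same measure as outcome 2, and that no domain-level decision rule exists beyond what the documents show. It does not depend on whether the steps and the activity minutes share a device.

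### BP control is measured only as change in hypertension stage, a bounded score, and the plan does not say how baseline stage enters the model; adjusting for it would gain power at no cost in patients

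*Combined protocol and SAP*

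**What the plan says.** Study Objectives gives BP control an aim of its own: "Secondary Aim: Evaluate efficacy of LTGO on BP control from baseline to 3 and 6 months post-randomization". The outcome list, under Protocol changes to primary outcomes due to COVID, provides two measures for it, "11. Secondary outcome: Blood Pressure Control, Change in stage of hypertension from baseline to 3 months" and "12. Secondary outcome: Blood Pressure Control, Change in stage of hypertension from baseline to 6 months". No BP value in mmHg and no other BP measure is listed.

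Statistical Considerations states the power once for all outcomes, "to achieve 80% power to detect an effect size as small as 0.64", and ties it to change: "for measures of the difference between LTGO and EUC groups in change in physical function, physical activity, and blood pressure control". The only model named appears in the software sentence: "All the analyses, including exploratory data analysis and linear mixed model, will be conducted by using SAS". No covariates are listed, and nothing says whether baseline is a covariate, a repeated outcome or simply subtracted. Baseline variables appear only in a check of randomisation: "The two groups were compared with respect to baseline variables using Student t-test or Mann-Whitney U test for continuous variables", with the matching tests for categorical variables.

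Study Design & Methods describes "a blocked randomization scheme stratified by sex, and length of transplant-hospital stay". Neither BP nor hypertension stage is a stratification factor.

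**The concern.** Stage is an ordered score with few levels. A participant in the lowest stage cannot fall and one in the highest cannot rise, so change in stage is tied to baseline stage by construction. Subtracting baseline does not remove this dependence, and it carries the baseline noise into the outcome. Regressing on baseline stage removes the part of the variance that baseline explains.

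Two things are at stake. The first is power for the aim's only measure: the trial must already hold baseline stage in order to compute change, so the gain needs no patients and no new data. The second is conditional bias. If the groups happen to differ in baseline stage, neither the stratification nor any stated model term corrects for it; the planned baseline comparison would reveal the imbalance but leave the estimate as it was.

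Naming a linear mixed model does not settle the matter. Some versions of that model adjust for baseline and others do not, and the plan does not say which is meant.

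**Working it through.** **1. Inputs.** From the documents: 40 per group, 1:1 allocation, two-sided alpha 0.05, standardised effect 0.64, stated power 80%. Not in the documents, so assumed: normally distributed BP cut into 3, 4 or 5 stages (12 different splits), and a baseline-to-follow-up correlation ρ of 0.4 to 0.7.

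**2. The plan's own figure.** Noncentrality = 0.64 × √(40/2) = 0.64 × 4.472 = 2.86. With 78 degrees of freedom the two-sided t-test has 80.7% power (81.7% by the normal approximation). The stated 80% reproduces when 0.64 is the standardised difference in change, which is how the outcome list and Statistical Considerations read together.

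**3. Effect of adjustment, stage treated as a continuous score.** With equal variances:

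- variance of change = 2·SD²·(1 − ρ)
- variance after regression on baseline = SD²·(1 − ρ²)
- adjusted standardised effect = 0.64 × √[2(1 − ρ)/(1 − ρ²)] = 0.64 × √[2/(1 + ρ)]

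| ρ | Adjusted effect | Power, unadjusted change | Power, adjusted |
|---|---|---|---|
| 0.4 | 0.64 × √(2/1.4) = 0.765 | 80.7% | 92.2% |
| 0.5 | 0.64 × √(2/1.5) = 0.739 | 80.7% | 90.4% |
| 0.7 | 0.64 × √(2/1.7) = 0.694 | 80.7% | 86.6% |
| 0.9 | 0.64 × √(2/1.9) = 0.657 | 80.7% | 82.6% |

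**4. Effect of adjustment, stage treated as categories.** Here ρ is the correlation of the underlying BP, and the treatment shift is solved so that the standardised difference in stage change is 0.64 (1,000,000 draws per cell). Unadjusted power is 80.7% by construction. Power adjusted for baseline stage runs from 86.8% (stages split 10/15/30/45%, ρ = 0.7) to 99.4% (60/20/12/8%, ρ = 0.4), a gain of 6 to 19 points. The top value is an extreme floor case that needs a BP effect of more than 2 SD, so it marks the edge of the range and not a typical gain.

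**5. Does the choice of mixed model matter?** Simulated with a baseline and two visits, 40 per group, 4,000 trials per cell, 6-month contrast. The effect here is set at 0.64 SD of BP change, so the columns should be compared with each other and not with the stated 80%.

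| Split, ρ | t-test on change | Random intercept, baseline as outcome, free group means | Linear, adjusted for baseline stage | Proportional odds, adjusted |
|---|---|---|---|---|
| 4 equal, 0.4 | 67.6% | 68.9% | 85.6% | 86.2% |
| 4 equal, 0.7 | 64.1% | 65.5% | 72.4% | 73.8% |
| 60/20/12/8, 0.4 | 41.7% | 44.8% | 68.1% | 71.0% |
| 60/20/12/8, 0.7 | 40.5% | 42.8% | 55.1% | 59.0% |

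The free-means mixed model stays within about 3 points of the unadjusted t-test. Baseline adjustment supplies nearly all the gain; proportional odds adds at most 3.9 points. By contrast, a mixed model that keeps baseline as an outcome but gives both groups one baseline mean does adjust. At ρ = 0.5 with SD = 1, its contrast variance is 0.0375, equal to the regression value 2(1 − 0.25)/40, against 2 × 2(1 − 0.5)/40 = 0.0500 for change.

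**6. Type I error.** With no true effect (40,000 trials per cell), overall rejection is 4.7–5.3% unadjusted and 4.8–5.2% adjusted. In the 13.4–14.1% of trials where baseline stage differs between groups by |t| ≥ 1.5, it is 10.2–16.9% unadjusted and 4.7–5.4% adjusted. In a separate run (20,000 trials per cell), the remaining trials reject 3.2–4.3% of the time unadjusted, which is how the overall rate stays near 5%.

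**The case against.** The strongest reply is that the plan is silent and does not specify an unadjusted test. It names a linear mixed model, and one with a common baseline mean would adjust implicitly. This stands, so the loss of power is conditional on how the model is fitted. It still leaves the choice open for the aim's only measure.

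The same silence covers every change outcome, including the primary ones. That also stands. BP control is a clear case because its score is bounded and has few levels, but the remedy should not stop there.

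A reader might infer that the power claim fails for BP control, or that 80% is right only if 0.64 refers to stage change. The documents do not support this. Their literal reading is stage change, where the figure reproduces. If 0.64 were in SDs of stage at a single visit, unadjusted change would still reach 80% once ρ is about 0.49, and the adjusted analysis would do so at any ρ from 0 upward. Even with 0.64 placed on BP change, which the outcome list does not suggest, the adjusted analysis reaches 80% in 16 of 48 cells examined.

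A reader might also infer inflated false positives from the 10–17% figure. It applies only to trials selected for chance imbalance and is conditional bias; the overall rate is about 5%.

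Finally, the magnitudes depend on assumptions, and stage is a legitimate definition of control. Both are true. The direction of the gain was the same in every cell examined, and the fix keeps stage as the outcome.

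**Conclusion.** The point holds as an unspecified baseline adjustment that should be settled. On the literal reading of 0.64, adjusting for baseline stage moves power from 80.7% to about 87–99%, given normal BP, 40 per group and ρ of 0.4–0.7. With ρ near 0.9 the continuous approximation leaves a gain of only about 2 points (82.6% − 80.7%). The documents give no staging cut-points, stage distribution or correlation, so these sizes are illustrative.

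Adjustment also removes the conditional bias when baseline stage is imbalanced by chance; it does not change overall type I error. The stated power figure and the sample size stand. This is worth doing because it is free, but it concerns efficiency on a secondary outcome and does not threaten the trial's validity.

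**What to change.** Keep outcomes 11 and 12 as worded, and state the staging definition and the scores given to the stages. In the linear mixed model already named, analyse stage score at 3 and 6 months on group, visit, group-by-visit, baseline stage and baseline-by-visit. The group estimate at each visit is the same whether the outcome is follow-up stage or change in stage. Writing change as Y − B = a + τ·group + b·B is identical to Y = a + τ·group + (b + 1)·B, with the same τ.

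Specify the corresponding baseline adjustment for the other change outcomes, where the plan is equally silent.

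Much of the document is written in the past tense. If outcomes have already been seen by arm, label the adjusted analysis post hoc and report the unadjusted stage change beside it.

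The cost is SAP wording and a few model terms in software already named; no patients or new measurements are needed. The downside is that stage scores assume equal spacing. A proportional-odds model at each visit, adjusted for baseline stage, can check this as a sensitivity analysis. It should not be the main test because it can fail when stages are sparse: in the extreme floor case above (60/20/12/8%, ρ = 0.4) it gave no stable estimate in 87% of simulated trials, against 0–2% in the other seven cells tried. The power statement needs no edit.
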